The planned study consists of focus group discussions designed to qualitatively assess knowledge, attitude and perception of people with hypertension and/or diabetes regarding air and noise pollution and its health effects in India. Participants will include about 40 adults, between the ages of 18 and 70, from a semi-urban community in the town of Dalkhola, Uttar Dinajpur district, West Bengal, India. Each semi-structured focus group will consist of 6 to 8 participants and is expected to last around 45 to 60 minutes. We plan to have a total of 6 (*n*=36-48) group discussions. To facilitate discussion, we will use a semi-structured guide that employs key concepts from the literature. Sessions will be led in the local language, Bengali, and will be digitally recorded. Recordings will be translated to English, and transcribed verbatim in English.

Focus groups will be performed in Dalkhola, at a local community hall that is accessible and convenient for all participants. The focus group leaders will be one of the investigators ([name]/[name]), with assistance from the study coordinator.

Participant recruitment:

We will be recruiting 2 sets of individuals: 1) Participants who were enrolled in the personal protective aids study and 2) Participants from the same ward/unit who were not enrolled in the personal protective aids study.

Inclusion criteria:

1. Individuals with hypertension and/or diabetes, between the ages of 18 and 70

Exclusion criteria:

- 1. Individuals who are deemed unable to actively participate in the focus group discussions
- 2. Individuals who refuse consent

Basis for sample size of 36-48:

We want to conduct 6 focus group discussions, with the composition as enclosed. We believe this number will allow the representation of sufficiently diverse perspectives on hypertension and diabetes. Each focus group discussion will have 6-8 participants, resulting in an estimated size of 36-48 participants. Since the study is primarily qualitative, no sample size calculations are required as we are not powering the study for any quantitative outcomes.

Procedure:

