After written/verbal informed consent is obtained, a trained interviewer will initiate the focus group discussion, based on the guide (below). A second person in the room will take notes on nonverbal cues. The entire discussion will be recorded for data analysis and study of non-verbal cues. At the conclusion of the focus group, all subjects will be given Rs 100/- as a token of appreciation.

The planned 6 groups are as follows-

Participants from personal protective aids study:

- 1) High adherence to DM and/or HTN medicines (Men and women)
- 2) Low adherence to DM and/or HTN medicines- Women
- 3) Low adherence to DM and/or HTN medicines- Men

Participants from the same ward/unit who were not a part of personal protective aids study:

- 4) High adherence to DM and/or HTN medicines (Men and women)
- 5) Low adherence to DM and/or HTN medicines- Women
- 6) Low adherence to DM and/or HTN medicines- Men

* Low adherence includes participants who have not sought a physician's opinion for management of their hypertension and/or diabetes

Analysis:

Qualitative data will be collected, transcribed, and associated with quantitative data such as demographics and treatment adherence. Using qualitative description analysis, researchers will evaluate responses independently to identify patterns, themes, important features and commonalities and differences. They will also develop codes for the data relevant to study variables. MAXQDA software will be used to manage data and assist in code development. The investigators will discuss and resolve coding discrepancies. Quantitative data will be described by frequencies, proportions, means or medians, and focus group themes will be compared using Pearson chi-squared test or Fisher exact test.

Reference:

- Hänninen Otto, Knol Anne B., Jantunen Matti, Lim Tek-Ang, Conrad André, Rappolder Marianne, et al. Environmental Burden of Disease in Europe: Assessing Nine Risk Factors in Six Countries. Environ Health Perspect. 2014 May 1;122(5):439–46.

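### Aim 2 tests focus-group themes with chi-squared or Fisher tests, but names no unit of analysis and makes no allowance for dependence within the six discussions

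*Combined protocol and SAP*

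**What the plan says.** Study Aim 2, Analysis, describes coding and qualitative description, then ends with a commitment to inference: "focus group themes will be compared using Pearson chi-squared test or Fisher exact test". The nearest it comes to a unit of analysis is that the qualitative data will be "associated with quantitative data such as demographics and treatment adherence", which does not settle whether the linkage is per person, per statement or per group. It gives no contrast and no significance level.

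Study Aim 2, Design and Method, sets the structure: "Each semi-structured focus group will consist of 6 to 8 participants". The sample-size paragraph adds "Each focus group discussion will have 6-8 participants, resulting in an estimated size of 36-48 participants", and states that "no sample size calculations are required as we are not powering the study for any quantitative outcomes".

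The Procedure section lists the six groups. Three are drawn from the trial and three from people in the same area outside it. Each set of three has one mixed-sex high-adherence group, one low-adherence group of women and one low-adherence group of men.

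The only method for correlated data in the document, GEE, is stated under the Aim 1 Analysis and is not extended to Aim 2.

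**The concern.** Pearson's chi-squared and Fisher's exact test both treat each counted item as independent. People in a focus group are not independent: one person raises a theme and others take it up or let it drop. The design then makes this matter. Every member of a group shares the same trial status and the same adherence category, so those two contrasts compare whole discussions, and whatever is peculiar to a discussion goes straight into the difference being tested.

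The choice of unit also largely decides the answer. Counting persons gives 36 to 48 observations and an error rate that is not guaranteed. Counting groups gives six observations and almost no resolution. Counting coded statements adds repeated counts from the same person on top of the group effect. With the unit left open, it could be chosen after the data are seen.

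At stake is a published p-value that presents a difference in attitudes between trial and non-trial participants, or between adherence groups, when it reflects only how a few discussions went.

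**Working it through.** **Inputs from the documents.** Six groups; 6 to 8 people per group; trial v non-trial is 3 v 3 groups; high v low adherence is 2 v 4 groups.

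**Assumptions, not in the documents.** A two-sided 0.05 level (stated only for the Aim 1 sample sizes); the ICC, shown from 0 to 0.3; theme prevalence of 20, 30 or 50%.

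**The plan's own figure.** 6 × 6 = 36 and 6 × 8 = 48, so the stated 36–48 reproduces.

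**Persons as the unit.** The design effect is 1 + (m − 1) × ICC. With m = 7 and ICC 0.1 it is 1 + 6 × 0.1 = 1.6, so 42 people carry the information of 42 / 1.6 ≈ 26.

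For the type I error, let the count of people raising a theme in a group of m be beta-binomial with prevalence p and parameters a = p(1 − ICC)/ICC and b = (1 − p)(1 − ICC)/ICC. Use the same distribution for all six groups, so that there is no true difference. Convolve the counts over the groups on each side of the contrast and add the probability of every 2 × 2 table with p < 0.05. This is exact enumeration, not simulation. Pearson is without continuity correction; Fisher is two-sided.

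Groups of 7, prevalence 50%, type I error (%):

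| ICC | 3 v 3 Pearson | 3 v 3 Fisher | 2 v 4 Pearson | 2 v 4 Fisher |
|---|---|---|---|---|
| 0 | 4.6 | 2.0 | 6.3 | 3.9 |
| 0.01 | 5.3 | 2.4 | 7.1 | 4.5 |
| 0.05 | 8.3 | 4.2 | 10.4 | 7.2 |
| 0.1 | 12.1 | 6.9 | 14.6 | 10.7 |
| 0.2 | 19.5 | 12.7 | 22.1 | 17.7 |
| 0.3 | 26.0 | 18.4 | 28.6 | 24.0 |

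Range over both contrasts, groups of 6, 7 or 8 and the three prevalences (%):

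| ICC | Pearson | Fisher |
|---|---|---|
| 0 | 4.6–6.5 | 2.0–3.9 |
| 0.01 | 5.2–7.2 | 2.4–4.5 |
| 0.05 | 7.4–10.6 | 3.7–7.2 |
| 0.1 | 10.3–15.2 | 5.7–10.7 |
| 0.2 | 15.8–23.3 | 10.1–17.7 |
| 0.3 | 20.9–30.0 | 14.7–24.4 |

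The ICC 0 rows are the baseline: uncorrected Pearson can exceed 5% from discreteness alone. The excess over that row is the effect of dependence.

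**Groups as the unit.** Score each group as showing the theme or not.

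- 3 v 3, complete separation, table [3,0 / 0,3]: Fisher p = 2/20 = 0.10. Pearson chi-squared = 6 × (3 × 3)² / (3 × 3 × 3 × 3) = 6.0, p = 0.014, with every expected count 1.5.
- 2 v 4, complete separation, table [2,0 / 0,4]: Fisher p = 1/15 = 0.067. Pearson chi-squared = 6 × (2 × 4)² / (2 × 4 × 2 × 4) = 6.0, p = 0.014, with expected counts from 0.67 to 2.67.
- Next most extreme table, [3,0 / 1,2] or [2,0 / 1,3]: Pearson chi-squared = 6 × 6² / 72 = 3.0, p = 0.083.

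So Fisher can never reach 0.05. Pearson reaches it only at complete separation, where all expected counts are well below 5. With independent groups and prevalence 50%, the exact error of that Pearson test in the 3 v 3 contrast is 2/64 = 3.1%. The group-level problem is therefore lack of resolution and p-values that cannot be trusted, not an inflated error rate.

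**The case against.** The strongest reply is that little rests on these tests. Aim 2 states no hypothesis, outcome or alpha, its main analysis is qualitative, and the plan says openly that it is unpowered for quantitative outcomes. That stands, and it limits the point to minor. It does not justify the tests: lack of power explains a missing sample-size calculation but does not protect the type I error.

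Second, the harm depends on an ICC that the documents do not give. This also stands. At an ICC of 0.01 Fisher stays below 5% throughout the range examined, and at 0.05 in the 3 v 3 contrast (groups of 7, 50% prevalence) it is still 4.2%. The error is best described as not guaranteed, rather than certainly inflated, and calling it material from about 0.1 is a judgement. The missing unit and comparison do not depend on any ICC.

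Third, the linkage to demographics and adherence suggests that persons were meant, which would make the group-level results less relevant. It suggests this without settling it, and the person-level reading is the one with the false-positive risk.

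Fourth, dropping the tests goes further than naming the unit and stating the limitation. But naming the unit alone leaves a test that is unprotected at person level if the ICC is material, or nearly uninformative at group level. A descriptive report avoids both.

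**Conclusion.** The concern holds and is minor. The plan commits to tests that assume independence, on data from six interacting groups, with no stated unit, no stated comparison and no allowance for clustering. With persons as the unit, whether the error is close to nominal or several times 5% turns on the unknown ICC. With groups as the unit, the tests have almost nothing to say.

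The figures rest on an assumed 0.05 level, ICC and theme prevalence, and apply to the trial-status and adherence contrasts. They do not cover contrasts that vary within a group, such as age, and counting by coded statement was not quantified. Confidence is medium because the size depends on the ICC. The Aim 1 outcomes are unaffected.

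**What to change.** In Study Aim 2, Analysis, replace the clause on testing themes with:

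> Themes will be reported descriptively in a theme-by-group matrix (each theme against the six groups) with illustrative quotations; no hypothesis tests will be done on themes.

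If the sponsor prefers to keep a test, the section should state the unit (person, coded statement or group) and the comparison, and label the p-values exploratory and not adjusted for clustering within groups. This discloses the weakness but does not remove it. A cluster-robust method is not a good way out, because such methods are unreliable with six clusters.

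The cost is one clause. Data collection and staffing do not change. The sponsor gives up, or relabels as exploratory, p-values in an aim that the plan itself treats as primarily qualitative.
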